
40% less patient-controlled opioid analgesia use than controls during the 48-hour post-operative period, with lower pain ratings^{26, 27, 30}. This series of studies was the first to demonstrate the potential of brain stimulation technology to be part of a standard post-operative pain-management strategy, however TMS is more complicated to deliver than tDCS, has more adverse events, and is more cumbersome in the post-operative setting. In two independent preliminary pilot studies, the PI has shown that tDCS can reduce post-operative PCA use by as much as 46% while simultaneously reducing subjective pain ratings. Thus, a handful of preliminary studies have demonstrated the potential for brain stimulation techniques to adjunctively manage post-operative pain, but a more definitive trial is needed to evaluate the efficacy of tDCS using a more rigorous experimental design. Further more data is needed to determine optimal tDCS dosing parameters before tDCS will become a viable clinical intervention for post-operative pain across surgical specialties.

Aim-1: Determine the effects of transcranial direct current stimulation (tDCS) on post-operative pain, patient-controlled analgesia (PCA) use, and post-surgical complications during the 48-hour post-operative period following total knee arthroplasty (TKA) or total hip arthroplasty (THA).

Hypothesis 1: Real tDCS (over sensory/motor and dorsolateral prefrontal cortices) will be associated with decreased PCA morphine-equivalent usage (primary outcome), decreased pain ratings (secondary outcome), and decreased post-operative complications compared to sham tDCS.

Aim-2: Collect preliminary data regarding dose-dependent effects of tDCS on post-operative pain, PCA morphine-equivalent usage, and 6-month outcomes.

Hypothesis 2a: The analgesic benefits of tDCS will be dose dependent such that one 20-minute post-operative tDCS session will be superior to sham, two sessions will be superior to one session, and four sessions will produce the largest analgesic effects in the present study.

Hypothesis 2b: Patients receiving higher doses of real tDCS will evidence lower incidence (and dose) of 6-month opioid medication use, reduced pain, and better quality of life.

B. BACKGROUND AND SIGNIFICANCE

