tDCS Effects on Post-Procedural Pain Pilot:¹⁰² Recently, the PI conducted the first-ever pilot study on the effects of tDCS on post- Endoscopic Retrograde Cholangiopancreatography (ERCP) pain. Nineteen Caucasian females (mean age=37.2 StdErr=2.4) were enrolled. After ERCP, participants were randomly assigned to receive 20-minutes of tDCS with anode over the left-prefrontal cortex and cathode over the gut representation of the sensory cortex. No serious adverse events were associated with tDCS. Side-effects of tDCS were limited to tingling (42%), itching (47%) and mild stinging (11%) under the electrodes. Patients that received a single 20-minute dose of real tDCS used 22% less total hydromorphone than those that received sham at the end of the 24-hour inpatient post-procedural period (Cohen's $d=.38$). The slope of the cumulative PCA usage curve was significantly steeper in the sham tDCS group compared to real ($t(355)=10.80, p<.0001$). VAS pain scores suggested an arithmetic advantage for real tDCS compared to sham (not statistically significant likely due to limited power). *Results from this pilot feasibility study suggest that tDCS is safe, well-tolerated, and may be able to reduce post-ERCP opioid requirements without increasing subjective pain ratings.*

[figure not shown]
tDCS Effects on Post-Total-Knee-Arthroplasty (TKA) Pain Pilot: In a very recent preliminary pilot study, the PI randomly assigned 40 patients undergoing unilateral TKA to receive a total of 80 minutes of real ($n=20$) or sham tDCS ($n=20$) with the anode over the knee representation of the motor strip and cathode over the right dorsolateral prefrontal cortex. 20-minute tDCS treatments were delivered: 1) in the PACU, 2) 4 hours later, 3) the morning of post-operative day-1, and 4) the afternoon of post-operative day-1. VAS pain and mood ratings were collected every 4 hours following surgery provided that patients were awake. The slopes of the cumulative PCA usage curves were significantly different between groups, and those TKA in the real tDCS group used 44% less PCA dilaudid at 48-hours post-op ($p=.007$; Cohen's $d=1.0$). Despite significantly lower PCA dilaudid levels, VAS ratings of pain-on-average were also significantly lower in the real tDCS group ($t(37)=2.28, p=.029$). No adverse events or serious adverse events were encountered. There were no cases in which tDCS needed to be discontinued due to patient discomfort or tDCS-related complications.

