- 8) No psychiatric conditions except for depression and/or anxiety disorders as these are commonly seen in patients with chronic pain

Participants will be recruited by members of the research team from the Orthopaedic Surgery pre-operative clinic. Eligible and interested participants will be enrolled in the study during their hospital stay for TKA or THA and for the following 6-month follow-up period. Data will be psychosocial, pain and behavioral ratings, medical surgical outcomes and PCA opioid use. All data will be collected by the study investigators, clinicians and the research team.

Dependent Measures: See table-1 for the schedule of measurement.

THE BECK DEPRESSION INVENTORY (BDI) is a well-researched, brief, self-report depression screening instrument. It consists of 21-items that assess different aspects of depression (e.g., anhedonia, excessive guilt, suicidal ideation, vegetative symptoms, tearfulness).¹⁰³⁻¹⁰⁸ IF ITEM #9 (SUICIDAL IDEATION) IS ENDORSED, PARTICIPANTS WILL UNDERGO A FACE-TO-FACE SELF-SAFETY SCREEN (I.E., INTERVIEW ASSESSING IDEATION, INTENT, PLAN, MEANS) AND A REFERRAL WILL BE MADE TO MENTAL HEALTH SERVICES IF NECESSARY FOR FORMAL EVALUATION AND TREATMENT AS INDICATED.

THE BECK ANXIETY INVENTORY (BAI) is a well-researched, brief self-report anxiety screening instrument. It consists of 21-items that assess different aspects of anxiety experience (e.g., physiological, cognitive, behavioral).¹⁰⁹

THE BRIEF PAIN INVENTORY (BPI) is a 17-item self-report questionnaire designed to assess chronic pain intensity and the impact of pain on general functioning, relationships and mood.^{110, 111}

THE MCGILL PAIN QUESTIONNAIRE (MPQ) is a 21-item self-report scale designed to capture the quality and intensity of the pain experience.^{112, 113} Subjects are asked to place a mark next to appropriate descriptors of their pain. The descriptors are assigned scores and the values load onto 4 factors: 1) Sensory, 2) Affective, 3) Evaluative, and 4) Miscellaneous.

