VISUAL ANALOGUE SCALE (VAS) RATING SCALES anchored with "no pain" and "worst pain imaginable" will be collected twice daily during the inpatient stay to assess pain at its worst, pain at its least, pain on average, and pain 'right now'. Additionally, participants will rate pain "Unpleasantness" using VAS in order to assess the affective component of the pain experience. The same system will be used to assess changes in mood at its worst, mood at its best, mood on average and mood 'right now' but the anchors will be "extremely depressed, sad or agitated" and "extremely good mood." This VAS method of pain assessment was chosen because it can be administered numerous times each day and it is highly sensitive to changes in pain perception and mood. VAS ratings will be collected immediately prior to, during, and immediately following all physical therapy sessions (inpatient and outpatient) during the 3-month follow-up period.

DAILY PAIN DIARY: The diary will require participants to record their average pain rating, pain at its worst, pain at its least, Activity level, Mood, sleep from previous night, and the number of times prescription pain medications were taken that day. Participants will be asked to fill out this form each day at night for the first 8 weeks post-surgery.

KNEE FLEXION MEASURE: A Gollehon Extendable Goniometer will be used to measure degrees of knee flexion at each post-operative physical rehabilitation visit.

POSTOPERATIVE COMPLICATIONS will be defined as any event, illness or postoperative occurrence that negatively impacts the health, well-being or functioning of the patients enrolled in the trial (including but not limited to headaches, confusion, delirium, nausea, vomiting, infections, and cardio-vascular complications). These events are tracked by medical staff as part of routine care, and the information will be gathered and recorded in the research database as well as length-of-stay at the time of discharge.

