PATIENT CONTROLLED ANALGESIA (PCA) PUMP USAGE: After tDCS administration, patients will be started on a patient controlled analgesia (PCA) pump. For statistical analyses of PCA pump usage, morphine-equivalent analgesic dose will be calculated (e.g., 0.2 mg of hydromorphone = 1.0 mg of morphine). Initial PCA settings will consist of hydromorphone 0.2mg/dose with a lockout interval of 10 minutes. The 4-hour maximum dose will be 4.8mgs with no continuous infusion. If a patient does not tolerate hydromorphone, the PCA medication can be changed to a different opioid and morphine-equivalent dosing will be used. If pain is not adequately controlled, the patient will be reassessed by

study personnel prior to increasing the PCA dosing regimen. PCA pump usage will be downloaded from the PCA pump after discharge from the hospital.

MEDICAL OUTCOMES STUDY SHORT-FORM 36 HEALTH SURVEY (SF-36) is a 36-item measure of general health intended to capture quality of life, functional ability and well-being (mental and physical). The SF-36 will be administered pre-surgery, at discharge, 3-month and 6-month follow-up.

BEST GUESS QUESTIONNAIRE will be used to determine how accurately patients, raters and tDCS operators were able to assess which treatment the patient received. This will assess our success in masking the sham treatments. Any time a guess-confidence rating is greater than 8 (on a 0 to 10 numeric rating scale), the PI will follow-up with the participant and/or administrator in order to determine what factors contributed to this level confidence. If the guess is verified correct by the statistical support personnel and any valid systematic administrative factors are identified (e.g., the participant or tDCS administrator reports that the he/she overheard the device-masking assistant discussing the device configuration, accidentally viewed the randomization codes, or felt/heard some unique tDCS-induced sensations that led them to correctly guess the condition), the participant will remain enrolled in the study (and no feedback will be provided to the administrator or participant regarding whether the guess was correct in order to avoid providing information that may further jeopardize the blind in later subjects). The participant's data will be dropped from analyses and steps will be taken to correct the mask procedure.

Table 1. Overview of the measurement schedule for the proposed study (POD=post-operative day)

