Patients scheduled to undergo TKA or THA surgery at the Ralph H. Johnson VAMC will be recruited during their pre-operative visit in the Orthopedic Surgery Clinic. A letter of invitation will be mailed to perspective participants whom medical staff on the study feel may be eligible to participate in the approved research. These prospective subjects that will receive letters will be identified through clinic referrals from the Ralph H. Johnson VA in Charleston, Sc. A HIPAA waiver of authorization will be on file with the IRB giving the research team permission send IRB approved generic letters of invitation to perspective participants. Written-informed consent will be obtained during this pre-op visit.

Protection against Risks

There are 3 areas in which safeguards to protect subjects from undue risk require discussion. These include the procedures used to obtain informed consent, the procedures used to ensure confidentiality of the subjects' data, and the procedures used to minimize possible risks associated with the laboratory procedures.

Informed Consent. In the consent forms and discussions with an investigator, subjects are advised fully of the procedures to be used, the amount of time required of them, the research procedures that will be conducted, the possible risks and benefits of the procedures, their right to refuse participation in the study without prejudice, their right to terminate participation at any moment without prejudice, and the name and telephone number of the Principal Investigator. All subjects will be required to have capacity to consent.

Confidentiality of Subjects' Responses. In the informed consent form, subjects are told that the information they provide and all findings will be kept strictly confidential, with access limited to the research staff and the possible exception of state or federal regulatory personnel. No one but the project staff has access to the master list linking subjects' names to code numbers, and all information obtained is coded. The respective master lists are kept under strict lock and key.

Research Procedures. We have described above the potential risks of the research procedures. If the subject shows deterioration in their clinical status, we will stop him/her from proceeding in the study, and coordinate appropriate care with a physician at the Ralph H. Johnson VAMC.

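### The rule for clinical deterioration does not separate stopping tDCS from leaving the study, so patient-rated follow-up to 6 months could be lost for outcome-related reasons

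*Combined protocol and SAP*

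**What the plan says.** The rule is in Section E.2, Protection against Risks, under Research Procedures: "If the subject shows deterioration in their clinical status, we will stop him/her from proceeding in the study, and coordinate appropriate care". Deterioration is not defined, and nothing is said about data collection after the stop. The introduction to that subsection describes this topic as "the procedures used to minimize possible risks associated with the laboratory procedures".

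Other places bear on how the rule reads:

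- Section D, Participants, says that patients are "enrolled in the study during their hospital stay for TKA or THA and for the following 6-month follow-up period". Section E.1, Sources of Material, gives the same span.
- Section D, Best Guess Questionnaire, covers a verified unblinding. There "the participant will remain enrolled in the study", although that patient's data are dropped from analyses.
- Section D, Procedures and Flow, places the last tDCS sessions on post-operative day 1. It says in general terms that participants complete the measures at every follow-up point.
- Section D, Statistical Analysis and Power, answers drop-out and loss to follow-up by recruiting extra patients. It gives no method for missing data.
- Hypothesis 2b predicts, at higher doses of real tDCS, "lower incidence (and dose) of 6-month opioid medication use, reduced pain, and better quality of life".

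**The concern.** Stopping stimulation in a patient who is getting worse is plainly right. The difficulty is that the sentence stops the patient's progress through the study, not through the sessions, and the study includes 6 months of follow-up. A site that followed it to the letter would stop collecting ratings on the patients who are doing worst.

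That loss would not be random. Section D defines postoperative complications as essentially anything that harms the patient's health, well-being or functioning, and complications are among the outcomes listed for Aim-1. Clinical deterioration overlaps heavily with that definition, so the trigger for leaving sits close to a trial outcome. Extra recruits replace the numbers. They do not replace the particular patients lost, so the comparison that randomisation set up is not restored.

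**Working it through.** **Plan's own figure.** The plan attaches no number to the stopping rule. Its nearest figure is Aim-1 power above 0.80 (90 active against 30 sham, d = 0.70, alpha 0.016; two-sided assumed, since the plan does not say). The noncentrality is 0.70 × √(90 × 30 / 120) = 0.70 × 4.743 = 3.320 and the critical value is 2.409. Power is therefore Φ(3.320 − 2.409) = Φ(0.911) = 0.819, or 0.808 with the noncentral t. The figure reproduces. It assumes complete data on all 120 patients, and the fix below does not change it.

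**Step 1: scope of the rule.** The heading and introduction of the paragraph point to the research procedures. The wording points to the study, which elsewhere means the hospital stay plus 6 months. Where the authors wanted a patient kept in, after a verified unblinding, they wrote so; the deterioration rule has no such clause. After post-operative day 1 no tDCS remains, so a stop from then on could end only data collection. The text does not settle which reading is meant.

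**Step 2: what a literal stop would lose.** These are the patient-rated cells in Table 1 (BDI, BAI, BPI, SF-36, VAS, MPQ and pain diary):

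| Time | Cells per column | Total |
|---|---|---|
| Admission | 4 | 4 |
| PACU, POD-0, POD-1, POD-2 | 2 each | 8 |
| Discharge | 4 | 4 |
| 2, 4 and 8 weeks | 3 each | 9 |
| 3 and 6 months | 4 each | 8 |
| All | | 33 |

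- After discharge: 9 + 8 = 17 of 33. Any inpatient stop loses all 17.
- All cells lost after a stop following PACU: 33 − 6 = 27. Following POD-0: 33 − 8 = 25. Following POD-1: 33 − 10 = 23.
- Inpatient VAS columns lost in those three cases: 3, 2 and 1 of 4.

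These are scheduled table cells, not single ratings. Section D has VAS taken twice daily in hospital and around physical therapy, and the diary filled in nightly for 8 weeks, so one cell can stand for many ratings.

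**Step 3: what survives without patient contact.**

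- PCA dose, the primary outcome in Hypothesis 1, is downloaded from the pump after discharge.
- Complications: "These events are tracked by medical staff as part of routine care".
- Opioid use in follow-up rests on patient report but is verified by chart review.
- VAS pain, which Statistical Analysis and Power lists among the primary outcomes although Hypothesis 1 calls pain ratings secondary, needs the patient. So do BPI and SF-36 at 3 and 6 months, which carry pain and quality of life for Hypothesis 2b.

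**The case against.** The strongest reply is that the sentence was never meant to end participation. It sits in a paragraph about procedural risk, and the procedure is over by post-operative day 1. Complications are scheduled for recording to 6 months, which would make little sense if a serious complication removed the patient. Procedures and Flow makes no exception for stopped patients when it describes follow-up. This reading is plausible and may well be what the sponsor intends. It stands as a reason to call the problem unresolved wording and not a deliberate choice to discard follow-up. It does not remove the problem, because staff who act on the rule have only the wider wording in front of them.

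A reader might infer that stopped patients would also be dropped from the analysis or moved out of their arm. The documents do not support that. Statistical Analysis and Power uses group assignment as the predictor and excludes no stopped patients, and the only exclusion rule is the one for verified unblinding.

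It is also fair to say that deterioration remains undefined, so who is stopped is left to judgement. The proposed amendment does not cure that, but recording the time and reason makes it visible.

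**Conclusion.** The point holds as a cheap improvement, with medium confidence. It is conditional on the rule being followed as worded. In that case each patient stopped in hospital loses all 17 post-discharge patient-rated cells of 33, plus any inpatient VAS ratings after the stop. What is exposed is mainly Hypothesis 2b, under an aim described as preliminary, and the long-term secondary analyses. The Aim-1 effect is probably small, because PCA dose and complications do not depend on patient contact and only VAS pain does.

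A reader might try to bound the number affected from the TKA pilot, where "No adverse events or serious adverse events were encountered" in 40 patients, and go on to a maximum bias in VAS pain. The documents do not support this. Pilot adverse events are not clinical deterioration, and the pilot placed the anode over the motor strip, not at F3. Nor does the bound limit a difference between arms: zero of 40 gives a one-sided 95% upper limit of 1 − 0.05^(1/40) = 7.2%, but zero of 20 in one arm gives 1 − 0.05^(1/20) = 13.9%. No deterioration rate is given, the number affected could be zero, and neither the size nor the direction of any bias can be determined.

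**What to change.** Amend the Research Procedures paragraph of Section E.2 so that clinical deterioration stops all further tDCS sessions, with hand-over to a physician as now, but does not end study participation. State that PCA download, complication recording, ratings where feasible and all scheduled follow-up to 6 months continue unless the patient withdraws consent. Record the time and reason for each stop. Add one line to Statistical Analysis and Power confirming that these patients stay in their randomised arm under the group-assignment analysis already planned.

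The cost is a sentence or two in Section E.2 and one line in the analysis section. The safety stop is unchanged. The downside is a few extra contacts with sicker patients, some of whom may be unable to give ratings. If the sponsor already intends this, the amendment simply records it.
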